### 11.2 Data Management Plan

A Data Management Plan (DMP) will describe procedures used for data review, data cleaning, and issuing and resolving data discrepancies. If appropriate, the Sponsor may update the DMP throughout the duration of the clinical investigation. The Sponsor will track and document control all revisions.

### 11.3 Source Documentation

Regulations and GCP require the Investigator to maintain information in the subject's original medical records that corroborates data collected on the CRFs. To comply with these regulatory requirements/GCP, sites should include the following information in the subject record at a minimum and if applicable to the clinical investigation:

- Medical history/physical condition of the subject before involvement in the clinical investigation sufficient to verify CIP entry criteria
- Dated and signed notes on the day of entry into the clinical investigation referencing the Sponsor, CIP number, subject ID number, and a statement that informed consent was obtained
- Dated and signed notes from each subject visit (for specific results of procedures and exams)
- Adverse events reported and their resolution, including supporting documents, such as discharge summaries, consult reports, office notes, X-ray results, lab results, and other source documents as applicable per the reported AE. The documentation of site awareness of SAEs and of investigator assessment of device relationship for SAEs should be included.
- Subject's condition upon completion of or withdrawal from the clinical investigation
- Any other data required to substantiate data entered into the CRF
- Patient reported outcome measures may be completed using CRF worksheets and can serve as the source documentation

## Clinical Investigation Plan

### 11.4 Case Report Form Completion

Site research personnel trained on the CIP and CRF completion will perform the primary data collection clearly and accurately based on source-documented hospital and/or clinic chart reviews. The investigator will ensure accuracy, completeness, legibility, and timeliness of the data reported to the Sponsor on the CRFs and in all required reports.

Sites will collect data on all subjects enrolled into the clinical investigation.

Only authorized site personnel will be permitted to enter the CRF data through the EDC system deployed by the Sponsor. The Sponsor will use an electronic audit trail to track any subsequent changes of the entered data.

### 11.5 Record Retention

The Sponsor and Investigator/Site will archive and retain all documents pertaining to the clinical investigation as per the applicable regulatory record retention requirements. The Investigator must obtain permission from Sponsor in writing before destroying or transferring control of any clinical investigation records.

## **12.0 ETHICAL CONSIDERATION**

### 12.1 Institutional Review Board/Medical Ethics Committee Review and Approval

The Principal Investigator at each investigational site will obtain IRB/EC approval for the CIP and ICF provided to the patient prior to consenting and enrolling patients in this clinical investigation. The site must receive the approval letter prior to the start of this clinical investigation and provide a copy to the Sponsor.

Sites will submit any amendments to the CIP as well as associated ICF changes to the IRB/EC and written approval obtained prior to implementation, according to each institution's IRB/EC requirements.

No changes will be made to the CIP or ICF or other written information provided to the patient without appropriate approvals, including IRB/EC, the Sponsor, and the regulatory agencies (if applicable).

Until the clinical investigation is completed, the Investigator will advise his/her IRB/EC of the progress of this clinical investigation, per IRB/EC requirements. Written approval must be obtained from the IRB/EC yearly to continue the clinical investigation, or according to each institution's IRB/EC requirements.

Sites will not perform any investigative procedures, other than those defined in this CIP, on the enrolled subjects without the written agreement of the IRB/EC and the Sponsor.

## **13.0 CLINICAL INVESTIGATION CONCLUSION**

The clinical investigation will be concluded when:

- The final report has been provided to investigators or the Sponsor has provided formal documentation of clinical investigation closure
- All sites are closed

The clinical investigation report will be submitted within one year of the end of the clinical investigation, or if applicable, will be submitted to the appropriate authorities according to current regulatory guidelines.

## Clinical Investigation Plan

### 14.0 PUBLICATION POLICY

The data and results from the clinical investigation are the sole property of the Sponsor. The Sponsor shall have the right to access and use all data and results generated during the clinical investigation. The Investigators will not use this clinical investigation-related data without the written consent of the Sponsor for any purpose other than for clinical investigation completion or for generation of publication materials, as referenced in the Clinical Trial Agreement. Single-center results are not allowed to be published or presented before the multi-center results. The Sponsor must review and approve any proposals for publications or presentations by the investigators in a timely manner in compliance with the Sponsor's publication policy set forth in the Clinical Trial Agreement.

The Sponsor will be responsible for determining whether to register the clinical investigation on [www.clinicaltrials.gov](http://www.clinicaltrials.gov) or any other clinical trials, in accordance with the International Committee of Medical Journal Editors guidelines, or any other applicable guidelines. In the event the Sponsor determines that the clinical investigation should be registered, the Sponsor shall be responsible for any such registration and results posting as required by the ClinicalTrials.gov website. Institution and/or Principal Investigator(s) shall not take any action to register the clinical investigation.

### 15.0 RISK ANALYSIS

All devices and accessories used in this study are market-approved; please refer to the device-specific IFU for information on risks. All procedures in this study are considered standard-of-care, therefore there are no anticipated incremental risks to subjects participating in this study.

#### 15.1 Anticipated Clinical Benefits

There are no anticipated clinical benefits to subjects participating in this study, other than the benefits of receiving RFA.

#### 15.2 Foreseeable Adverse Events and Anticipated Adverse Device Effects

Risks associated with the specified lesion generator, procedure, and compatible accessories, are described in the IFU documents. The study does not require any additional procedures or assessments other than patient reported outcomes such as NRS, EQ-5D, and other questionnaires. There are no additional risks introduced to patients enrolled in the study.

An RFA procedure involves risks. In addition to the risks commonly associated with any invasive procedure, below are listed the anticipated potential adverse effects with the use of a RF Pain Management System:

- As a consequence of electrosurgery, damage to surrounding tissue through iatrogenic injury can occur.
- Nerve injury, including thermal injury, or puncture of the spinal cord or nerve roots, potentially resulting in radiculopathy, paresis, and paralysis.
- Pain, pulmonary embolism, hemothorax or pneumothorax, infection, unintended puncture wound, including vascular puncture and dural tear, hemorrhage, and hematoma.

## Clinical Investigation Plan

### 15.3 Residual Risks Associated with the Device Under Investigation, as Identified in the Risk Management Report / Risk Analysis Report

The clinical risks associated with RF Pain Management systems are well known. Any potential residual risks are outweighed by the benefits, and the overall residual risk was determined to be acceptable. Clinical evidence demonstrates acceptable safety and performance of the device and accessories under this post-market study.

### 15.4 Risks Associated with Participation in this Clinical Investigation

The risks involved with this study are comparable to those associated with the use of any other commercially available RF Pain Management system.

### 15.5 Steps Taken to Control or Mitigate Risks

The Sponsor will employ measures throughout the course of this study to minimize these risks such as clearly defined inclusion and exclusion criteria to ensure that only appropriate subjects are enrolled, proper consenting process, selection of investigational sites that have a sufficient level of clinical expertise, investigator selection, and appropriate training for all involved in the study activities. In-depth recommendations, special warnings and precautions, and device handling are included in IFU documents of the lesion generator and accessories included in this study. All device-related adverse events and device deficiencies will be reported to the Sponsor and will be monitored internally for safety surveillance purposes.

### 15.6 Risk to Benefit Rationale

The risks associated with Abbott's IonicRF lesion generator system and compatible accessories are anticipated to be comparable to those associated with the use of other commercially available RF Pain Management system. The patients participating in this study are indicated for using a RF Pain Management system as part of their standard medical management and are subject to the risks associated with these devices.

## Clinical Investigation Plan

### APPENDIX I: ABBREVIATIONS AND ACRONYMS

AE	Adverse Event
CE	Conformité Européenne
CFR	Code of Federal Regulations
CIP	Clinical Investigation Plan
CRF	Case Report Form
EC	Ethics Committee
EDC	Electronic Data Capture
EU	European Union
EQ-5D	EuroQol – 5 Dimensions
FDA	Food and Drug Administration (US)
HIPAA	Health Insurance Portability and Accountability Act
IFU	Instructions for Use
IRB	Institutional Review Board
ISO	International Organization for Standardization
M.D.	Medical Doctor
MDR	Medical Devices Regulation
MHRA	Medicines and Healthcare products Regulatory Agency (UK)
NDI	Neck Disability Index
NRS	Numerical Rating Scale
ODI	Oswestry Disability index
OUS	Outside of United States
PGIC	Patient Global Impression of Change
PMDA	Pharmaceuticals and Medical Devices Agency (Japan)
PRO	Patient Reported Outcome
PROMIS	Patient-Reported Outcomes Measurement Information System
RF	Radiofrequency
RFA	Radiofrequency Ablation
SAE	Serious Adverse Event
SADE	Serious Adverse Device Effect
US	United States
VAS	Visual Analogue Scale
WOMAC	Western Ontario and McMaster Universities Osteoarthritis Index

## Clinical Investigation Plan

### APPENDIX II: SITE CONTACT INFORMATION

A list of Clinical Investigational sites will be kept under a separate cover and is available upon request.

## **Clinical Investigation Plan**

### **APPENDIX IV: LABELS**

IFU documents will be kept under a separate cover and are available upon request.

## Clinical Investigation Plan

### APPENDIX V: CASE REPORT FORMS

Case Report Forms will be kept under a separate cover and are available upon request.

## Clinical Investigation Plan

### APPENDIX VI: INFORMED CONSENT FORM

The study specific sample Informed Consent Form will be kept under a separate cover and is available upon request.

## Clinical Investigation Plan

### APPENDIX VII: MONITORING PLAN

A copy of the Monitoring Plan can be obtained upon request from the Sponsor Clinical Project Manager for the clinical investigation.

## Clinical Investigation Plan

### APPENDIX VIII: REVISION HISTORY

This CIP may be amended as appropriate by the Sponsor. Rationale will be included with each amended version in the revision history table below. The version number and date of amendments will be documented.

IRB/EC and relevant Regulatory Authorities, if applicable, will be notified of amendments to the CIP.

## Clinical Investigation Plan

### APPENDIX IX: CIP SUMMARY

Clinical Investigation Name and Number	ROSTRA (CRD_1029)
Title	Real-World Outcomes Study on Subjects Treated with Radiofrequency Ablation
Objective	The objective of this study is to collect real-world safety and effectiveness data on Abbott's IonicRF™ Generator and compatible RFA accessories. This post-market study is intended to satisfy EU MDR requirements.
Device Under Investigation	IonicRF Radiofrequency Generator, along with any country-specific market-released accessory (i.e. electrode, cannula, grounding pad, and adaptor cable) compatible with the IonicRF Generator.
Number of Subjects Required for Inclusion in Clinical Investigation	The study will enroll up to [REDACTED] patients at up to [REDACTED] sites in Europe and the US. Additional centers may be approached for participation in the study as needed.
Clinical Investigation Design	International, prospective, non-randomized, single-arm, multi-center, and post-market study
Primary Endpoints	
The primary effectiveness endpoint is the relative change in Numeric Rating Scale (NRS) [REDACTED] follow-up visit. NRS is the patient's self-rating of average pain intensity for the area being treated over [REDACTED] from 0 "no pain" to 10 "worst pain imaginable". This will be calculated for each represented indication.
 
The primary safety endpoint is the incidence of device- and procedure-related serious adverse events.

Subject Follow-up	Follow-up visit: Subjects will be followed at 3 and 6 months from the date of (last) RFA procedure
Inclusion Criteria for all candidate subjects	
 
1. Subject must provide written informed consent prior to any clinical investigation-related procedure
 
2. Subject is <math>\geq</math> 18 years of age
 
3. Subject has chronic pain <math>></math> 6 months and was unresponsive to conservative management
 
4. Subject has pain on an NRS scale of <math>\geq</math> 6
 
5. Subject is scheduled for an RFA procedure with the IonicRF generator within 30 days of baseline to treat chronic pain at one anatomical region
 
6. Subject has stable chronic pain medication use for 30 days
 
7. Subject is willing and able to comply with the prescribed follow-up evaluations
 

## Clinical Investigation Plan

Exclusion Criteria for all candidate subjects	
 
1. Subject is currently participating in another clinical investigation that may confound the results of this study
 
2. Ongoing systemic or local infection in the area of the procedure
 
3. Recent use of anticoagulants or subject with coagulopathy
 
4. Primary complaint of deafferentation pain
 
5. Presence of other anatomic or comorbid conditions, or other medical, social, or psychological conditions that, in the investigator's opinion, could limit the subject's ability to participate in the clinical investigation or to comply with follow-up requirements of the clinical investigation results
 
6. Subject's opioid usage is > 90 morphine equivalents per day
 

Inclusion criteria for candidate subjects with facet joint pain (lumbar, cervical)	
 
1. Subject has unilateral or bilateral pain on para-spinal palpation and localized pain with extension/lateral bending
 
2. Subject has facet joint pain confirmed by at least 1 positive medial branch block with 0.5 mL or less of anesthetics (across at least 3 vertebral levels) achieving at least 50% pain relief, with real-time injection of radiographic contrast under fluoroscopic guidance
 

Inclusion criteria for candidate subjects with sacroiliac pain	
 
1. Subject has sacroiliac joint pain based on medical history and physical exam
 
2. Subject has sacroiliac joint pain confirmed by an infiltration of local anesthetics in the posterior part of the sacroiliac joint achieving at least 50% pain relief
 

Inclusion criteria for candidate subjects with radicular pain	
 
1. Subject has radicular pain based on medical history and physical exam
 
2. Subject has radicular pain confirmed by dermatomal mapping corresponding to at least 1 nerve root level
 

Eligibility criteria for candidate subjects with trigeminal neuralgia	
Inclusion:
 
 
1. Subject has trigeminal pain based on medical history and physical exam
 
2. Subject did not have any mass effect or stroke causing trigeminal pain confirmed by MRI
 
3. Subject is <math>\geq 60</math> years of age in case of neurovascular conflict
 
 
Exclusion:
 
 
1. Subject has sensory problems
 

Inclusion criteria for candidate subjects with knee or hip pain	
 
1. Subject has knee or hip pain based on medical history and physical exam
 
2. Subject has radiographically confirmed osteoarthritis of the hip or knee, or has chronic pain following joint arthroplasty
 

1.0 SYNOPSIS OF STUDY DESIGN

1.1 **Purpose of the Statistical Analysis Plan**

This statistical analysis plan (SAP) is intended to provide a detailed and comprehensive description of the planned methodology and analysis to be used for **exercise**, the ROSTRA clinical investigation. This plan is based on the Version **Clinical Investigation** Plan.

1.2 **Clinical Investigation Objectives**

The objective of this study is to collect real-world safety and effectiveness data on Abbott's lonicRF[™] Generator and compatible accessories.

1.3 **Clinical Investigation Design**

This is an international, prospective, non-randomized, single-arm, multi-center, and post-market study. Subjects will be assessed at baseline and post implant using questionnaires. Specifically, assessments will include pain intensity as assessed by the Numeric Rating Scale (NRS), quality of life as assessed by EuroQol-5 Dimensions (EQ-5D) and PROMIS-29, and procedure satisfaction as assessed by the Patient Global Impression of Change (PGIC) and patient satisfaction level. The Oswestry Disability Index (ODI), Neck Disability index (NDI), and Western Ontario and McMaster Universities Osteoarthritis Index (WOMAC) index score will be completed for specific indications only.

Subjects will be followed via clinic visit or remote follow-up at the study will enroll up to subjects at up to sites in Europe and the United States. No site may enroll more than sites of the total subjects. This study uses a sample size that allows inclusion of multiple indications. Additional centers may be approached for participation in the study as needed.

It is recommended that subjects should limit increases in their prescribed chronic pain medications from Baseline to the assessment of the primary endpoint at Baseline to the assessment of the primary endpoint at Baseline to the types of medication and the prescribed maximum daily dosage of pain medication for their chronic pain condition should not increase significantly (at the discretion of the investigator). If a rescue medication is required, subjects will be allowed additional aspirin or Tylenol (Acetaminophen) at a maximal dose of 2 g within a 24-hour period. (NOTE: Post-operative pain medications prescribed only for acute management of post-procedural pain are allowed.)

Subject enrollment is expected to be completed within a subjects will be followed for **subjects**. The total duration of the study is expected to be **subjects**, including enrollment, data collection from all subjects, and study close out.

1.4 Endpoints

1.4.1 **Primary Safety Endpoint**

The primary safety endpoint is the incidence of device- and procedure-related serious adverse events by

1.4.2 Primary Effectiveness Endpoint

The primary effectiveness endpoint is the relative change in Numeric Rating Scale (NRS)

follow-up visit. NRS is the patient's self-rating of average pain intensity for the area being treated over from 0 "no pain" to 10 "worst pain imaginable". This will be calculated for each represented indication.

1.4.3 Secondary Endpoint

There are no specific secondary endpoints of this clinical investigation.

1.4.4 **Descriptive Endpoints**

Refer to Section 3.5 in this SAP.

1.5 Randomization

This is a non-randomized clinical investigation.

1.6 Blinding

This is a unblinded clinical investigation.

2.0 ANALYSIS CONSIDERATIONS

2.1 Analysis Populations

- 1. Full Analysis Set (FAS):
- 2. As-treated Population (AT):

The safety endpoints will be performed on the FAS. The effectiveness endpoints will be performed on the AT.

2.2 Statistical Methods

2.2.1 Descriptive Statistics for Continuous Variables

For continuous variables (e.g., age, change in NRS, improvement in patient outcome measures, etc.), results will be summarized with the numbers of observations, means, standard deviations, medians, minimums, maximums, and 95% confidence intervals for the means as per the table mockups.

2.2.2 Descriptive Statistics for Categorical Variables

For categorical variables (e.g. gender, race, etc.), results will be summarized with subject counts and percentages/rates, and where specified in the table mockups, with exact 95% Clopper-Pearson confidence intervals.

2.2.3 Survival Analyses

Survival analysis will be conducted to analyze time-to-event variables, if applicable. Subjects without

events will be censored at their last known event-free time point. Survival curves will be constructed using Kaplan-Meier estimates.

2.3 Endpoint Analysis

2.3.1 Primary Endpoint(s)

The primary effectiveness endpoint is

The null and alternative hypotheses are as follows:

 $H_0: \mu = 0$ $H_1: \mu \neq 0$

This endpoint will be evaluated and the second second second the second se

The primary safety endpoint is the incidence of device- and procedure-related serious adverse events

The device- and procedure-related serious adverse events will be summarized as frequency, proportion, and number of events per patient years of follow-up. The analysis will be performed on FAS as described in Section 2.1.

2.3.2 Descriptive Endpoints

Summary statistics will be presented for the descriptive endpoints. Refer to 2.2 for the descriptive summary statistics.

2.4 Sample Size Calculations

2.5 Interim Analysis

No formal interim analyses are planned for this study. As such, no formal statistical rule for early termination of the trial is defined. Interim report with descriptive analysis may be performed on an ad-hoc basis to assess continuing safety and effectiveness and provide routine updates to applicable authorities as necessary.

2.6 **Timing of Analysis**

The primary effectiveness and safety endpoints will be conducted when all enrolled subjects have . The final analysis

will be conducted, and final report will be written when the enrolled subjects

2.7 Study/Trial Success

Success will be declared when the primary endpoint is met.

2.8 **Subgroups for Analysis**

Subgroup analyses may be performed on an ad-hoc basis to understand outcomes for specific indications and patient populations.

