## 4.0 ENDPOINTS

### 4.1 Primary Effectiveness and Safety Endpoint

The primary effectiveness endpoint is the relative change in Numeric Rating Scale (NRS) [REDACTED] [REDACTED] follow-up visit. NRS is the patient's self-rating of average pain intensity for the area being treated over [REDACTED] from 0 "no pain" to 10 "worst pain imaginable". This will be calculated for each represented indication.

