## Clinical Investigation Plan

The primary safety endpoint is the incidence of device- and procedure-related serious adverse events.

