## Clinical Investigation Plan

### 5.0 SUBJECT SELECTION AND WITHDRAWAL

#### 5.1 Subject Population

This clinical investigation will enroll subjects of all genders from the general chronic pain population referred to participating pain clinics.

Indications include (approximately 20 subjects each):

- Lumbar facet joint pain
- Cervical facet joint pain
- Sacroiliac joint pain
- Radicular pain
- Trigeminal neuralgia
- Knee pain
- Hip pain
- Other pain

Patients must meet all general eligibility criteria and the eligibility criteria specific to the patient's chronic pain indication and provide written informed consent prior to sites conducting any investigation-specific procedures not considered standard of care.

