#### 8.2.1 Primary Effectiveness Endpoint Analyses

The primary effectiveness endpoint is [REDACTED]

The null and alternative hypotheses are as follows:

$$H_0: \mu = 0$$

$$H_1: \mu \neq 0$$

[REDACTED]  
[REDACTED]

This endpoint will be evaluated [REDACTED] at the 5% significance level. The endpoint will be analyzed based on AT population described in Section 8.1.

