#### 8.2.2 Primary Safety Endpoint Analyses

The device- and procedure-related serious adverse events will be summarized as frequency, proportion and number of events per patient years of follow-up. The analysis will be performed on FAS as described in Section 8.1.

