2.10 Multiplicity Issues

The analysis will be done by indication and no multiplicity adjustment will be applied.

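### Does SAP 2.7 need a rule for how many indications must show an effect before success is declared?

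*SAP*

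**What the plan says.** SAP 2.7 states: "Success will be declared when the primary endpoint is met". The sentence is complete and shows no sign of redaction.

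The effectiveness endpoint is the relative change in NRS. Protocol 4.1 adds: "This will be calculated for each represented indication"; SAP 1.4.2 says the same. Protocol 5.1 lists eight indications, the last being a mixed category of other pain, at about 20 subjects each. SAP 2.10, also intact, reads: "The analysis will be done by indication and no multiplicity adjustment will be applied".

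Protocol 8.2.1 gives one pair of hypotheses (mean equal to zero against not equal to zero). After a redacted stretch it says that the endpoint is evaluated "at the 5% significance level. The endpoint will be analyzed based on AT population described in Section 8.1". The definition of the mean and the description of the test are blacked out there and in SAP 2.3.1.

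Safety is also a primary endpoint: "The primary safety endpoint is the incidence of device- and procedure-related serious adverse events". Protocol 8.2.2 says that these "serious adverse events will be summarized as frequency, proportion and number of events per patient years of follow-up". No safety hypothesis or threshold is visible. In SAP 1.4.1 the safety definition breaks off at a redaction.

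SAP 2.8 and Protocol 8.5 describe analyses of specific indications as ad hoc subgroup analyses.

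**The concern.** A success rule should return one answer for any set of results. Here one declaration sits on top of as many as eight tests, and nothing visible says how they combine. If five indications rejected and three did not, a reader could argue for success, for failure, or for five separate successes. Left open, the choice could be made after the results are known, and the false-success rate would depend on it.

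The singular word for the endpoint raises a second question. The plan has two primary endpoints, and the safety one is only summarised, so on the visible text there is nothing for it to meet.

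At stake would be a headline claim of study success resting on one positive indication out of eight, with an error rate well above 5%.

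**Working it through.** The plan states no family-wise error rate, power, effect size or SD in visible text, so there is no plan figure to reproduce.

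**Inputs from the documents.** Up to k = 8 indications and about n = 20 in each (Protocol 5.1); two-sided 5% level (Protocol 8.2.1); no adjustment (SAP 2.10). Different indications contain different subjects, so the tests can be treated as independent.

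**Error rates if no indication has any effect**

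- Any one indication suffices, either direction: 1 − 0.95^8 = 0.337. With 5, 6 or 7 represented indications: 0.226, 0.265, 0.302.
- Any one suffices, benefit only: 1 − 0.975^8 = 0.183. With 5, 6 or 7: 0.119, 0.141, 0.162.
- At least two of eight: 1 − 0.95^8 − 8 × 0.05 × 0.95^7 = 0.057; benefit only (0.975 and 0.025 in place of 0.95 and 0.05), 0.016.
- All eight must reject: 0.05^8 = 3.9 × 10^-11. If only one null is true and the other seven tests are certain to reject, at most 0.05.
- Each indication judged alone: 0.05 per claim (0.025 for false benefit), as the plan states.

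The 33.7% figure counts significant worsening of pain as success. The figure that matters for a benefit claim is 18.3%. Both need a mean change of exactly zero in all eight groups, which is unlikely in a single-arm study that requires an entry NRS of at least 6 (Protocol 5.3.1.1).

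**How often would indications disagree?** This needs a mean and an SD, which the documents do not show. Assume n = 20, a one-sample t test, and the same true mean reduction in all eight. Power p for benefit comes from the noncentral t distribution with noncentrality √20 × mean/SD. The chance that some reject and some do not is 1 − p^8 − (1 − p)^8.

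| Assumed mean reduction | SD | p | Chance of disagreement |
|---|---|---|---|
| 30% | 30% | 0.989 | 0.088 |
| 30% | 40% | 0.889 | 0.610 |
| 30% | 50% | 0.721 | 0.927 |
| 40% | 30% | 0.9999 | 0.001 |
| 40% | 50% | 0.924 | 0.469 |
| 50% | 50% | 0.989 | 0.088 |

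The range runs from almost nothing to 93%, depending wholly on assumed inputs, so it cannot show that disagreement is likely.

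**Which reading does the intact text support?**

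1. *Per indication.* The endpoint is calculated by indication (Protocol 4.1, SAP 1.4.2) and analysed by indication without adjustment (SAP 2.10). The endpoint being met then means met for that indication. This fits all three sections, and it is the reading under which no adjustment is justified.
2. *Pooled.* Only one hypothesis pair is given, and SAP 2.8 and Protocol 8.5 treat indication-specific looks as ad hoc. A single pooled test is therefore partly open; under it no multiplicity arises and none of the figures above apply.
3. *Any one suffices.* No passage says this.
4. *All must reject.* No passage says this either, and it would not inflate error.

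**What would a rewording change?** Stating that success is declared for each indication separately leaves every test at 5%. The chance of at least one false benefit finding among eight true nulls stays at 1 − 0.975^8 = 18.3%. No estimate, interval or p-value moves.

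**Safety.** Only effectiveness has a hypothesis, so the singular endpoint in SAP 2.7 reasonably means effectiveness. Whether a safety threshold exists cannot be judged, because SAP 1.4.1 is cut by redaction.

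**The case for a change.** The strongest case for a change is that SAP 2.7 and 2.10 are both intact, and together they give one verdict on several tests. SAP 2.7 concerns success of the study, not of an indication, and does not say that success is per indication. The combining rule matters even when the device works. On the assumed 30% mean reduction with an SD of 40%, requiring all eight would succeed 0.889^8 = 39% of the time, while requiring any one would succeed almost always. The study is meant to meet EU-MDR requirements, so a declared success should be checkable, and one sentence written before the data are seen would cost nothing.

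Much of this stands as a remark on wording: the visible text does not say what success covers when indications differ. It does not stand as a fault in the design or analysis. The gap lies where text is blacked out, so whether a rule exists is unknown. An analyst following SAP 2.10 will report each indication with its own test and estimate, and readers will see any disagreement directly. The stated objective is to collect post-market safety and effectiveness data, and no visible text attaches a decision to an overall success claim. Protocol 8.9 requires major changes to the statistical plan to be made by amendment. That makes a change traceable, although it would not by itself prevent a choice made after seeing the data.

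**Conclusion.** The concern does not call for a change. SAP 2.7 is loosely worded, but the reading best supported by the intact text is success by indication at 5% each, and under that reading the lack of adjustment is sound. The 33.7% and 18.3% figures are correct for eight independent tests with every null true, but as study-level error rates they belong to a one-is-enough rule that no passage states. Clarifying the wording would alter no test and no error rate.

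This rests on two assumptions: that the redacted parts of Protocol 8.2.1 and SAP 2.3.1 do not set a one-is-enough rule for an overall claim, and that results are reported for each indication as SAP 2.10 says. If the redacted text did set such a rule, the 18.3% chance of a false benefit claim would apply and an adjustment would be needed.
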